9.4 Statistical Analysis Process

The study will be analyzed by the sponsor or its agent.

The statistical analysis plan (SAP) will provide the statistical methods and definitions for the analysis of the efficacy and safety data, as well as describe the approaches to be taken for summarizing other study information such as subject disposition, demographics and baseline characteristics, IP exposure, and prior and concomitant medications. The SAP will also include a description of how missing, unused and spurious data will be addressed.

The SAP will be finalized prior to unblinding to preserve the integrity of the statistical analysis and study conclusions.

All statistical analyses will be performed using SAS® (SAS Institute, Cary, NC 27513).

9.5 Planned Interim Analysis and Data Monitoring Committee

9.5.1 Planned Interim Analysis

Study enrollment will be paused after 92 subjects have been randomized in order for an IA to be conducted after at least 80 subjects have received 24 weeks of treatment. To protect study integrity, the IA will be performed by an independent statistician and statistical reporting group who are not involved in the clinical trial conduct and are not responsible for the final analysis of clinical trial data. The IA will be performed to evaluate the safety, tolerability, and efficacy of 3 doses of volixibat each compared to PBO and be used to drop 1 or more doses of volixibat, or to terminate the trial.

The criteria for deciding whether or not to continue randomizing to a particular volixibat dose following the Week 24 IA will be specified in the DMC charter. In general, randomization to any volixibat dose determined to be unsafe, intolerable or ineffective/futile at the IA will be discontinued. If all of the volixibat doses are determined to be intolerable or ineffective/futile the clinical trial will be terminated. If none of the volixibat doses are determined to be unsafe, intolerable or ineffective/futile then randomization to the volixibat dose that is the least promising or least helpful in characterizing the dose-response relationship (as specified in the DMC charter) will be discontinued. Tolerability will be assessed by comparing the number of discontinuations due to any one TEAE (presumably gastrointestinal events, most notably, diarrhea, loose stools, increased evacuations, and abdominal pain) between each volixibat dose group and PBO group. Efficacy will be assessed based on a reduction of steatosis (assessed by MRI-HFF) and ALT by comparing the change from baseline in MRI-HFF and percent change from baseline in ALT at Week 24 between each volixibat dose group and PBO group.

Subjects recruited into the study prior to the IA will continue with the same dosing regimen for the duration of the planned study participation. That is, a subject receiving a dose to which randomization is stopped after the IA will continue to receive that same dose throughout the course of the study, and complete all required assessments, unless a dose is determined to be unsafe, in which case the affected subjects would be discontinued from the study and followed as per Section 4.5. Subjects recruited into the study after completion of the IA will be randomized evenly to the remaining volixibat dose groups or PBO group by IRT. Subjects will be randomized to 1 or 2 volixibat doses or to PBO. Thus, depending on the results from the IA, the study may be terminated, or one or more doses of volixibat will be discontinued. If the study is not terminated, subjects will receive a total of 48 weeks of IP.

9.5.2 Data Monitoring Committee

An independent DMC will be established to assess safety, tolerability, and efficacy during the study, as well as to ensure the validity and scientific merit of the trial. The DMC will monitor ongoing data generated by the study at regular intervals for the duration of the study. Their role

is to protect the interests of the subjects in the study and of those still to be entered, by review of accumulating data generated in the study. If a safety concern is identified (eg, if either of the criteria are met in Section 4.5.4, Safety-related Stopping Rules), the DMC may recommend an action to the sponsor on further study conduct, including stopping the study at any time.

In addition, the DMC will review the results of the Week 24 IA and make recommendations concerning study discontinuation due to intolerance or futility, or the continued randomization of 1 or more volixibat dose groups and PBO.

The roles, responsibilities, and rules governing operation of the DMC will be discussed in full in a DMC charter. The DMC charter will define the primary responsibilities of the DMC; guide its activities, its relationship with other study components, its membership, and the purpose and timings of its meetings. It will provide the procedures for ensuring confidentiality, formal communication, and outline of the content of reports that will be provided by the DMC.

Appropriate summary statistics and data listings will be provided to the DMC by an independent statistician supported by an independent statistical reporting group not otherwise assigned to the study.

The recommendations made by the DMC to alter the conduct of the study or to stop the study will be forwarded to Shire for final decision. The implementation of any DMC recommendation is solely the responsibility of the sponsor. Shire will forward such decisions to regulatory authorities, as appropriate.

9.6 Sample Size Calculation and Power Considerations

These are the primary hypotheses that are being tested in this study:

- Null: The proportion of subjects at Week 48 with a reduction of at least 2 points without worsening of fibrosis from baseline NAS does not differ between any of the volixibat doses and PBO.
- Alternative: The proportion of subjects at Week 48 with a reduction of at least 2 points without worsening of fibrosis from baseline NAS does differ between at least one volixibat dose and PBO.

Response rates of 21% (PBO) and 45% (active) were reported in the FLINT trial ([Neuschwander-Tetri et al. 2015](#)) using the same primary end-point of reduction of NAS by at least two points (without worsening of fibrosis). Based on those response rates, 67 subjects per group completing the trial are needed for 80% power with a 10% type I error for a study comparing two volixibat doses to PBO. Holm multiplicity adjustment was included in the sample size estimate.

Approximately 334 subjects will be screened to enroll 266 subjects to achieve 201 completers. After enrollment of at least 80 subjects (20/treatment arm – 3 active and 1 PBO) a 24-week IA will eliminate at least one dose group based on the criteria provided to the DMC; enrollment will

continue to include approximately 67 subjects in each of the remaining arms. The sample size target for this study is 67 completers in each of the treatment groups (201 total if 3 arms continue). Including an additional 20 subjects to account for one dose dropped at the IA, 221 subjects are needed. Therefore, approximately 266 (accounts for 20% of 221 dropping out) subjects will be randomized if three arms (2 active and 1 PBO) continue. Fewer subjects are needed if more than one active dose is dropped.

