3. STUDY DESIGN

3.1 Study Design and Flow Chart

[figure not shown]
This study will be a Phase 2, 48-week, multicenter, double-blind, randomized, PBO-controlled, parallel group, proof of concept, dose-finding study, with one IA after 24 weeks of treatment. There will be 3 active arms of volixibat (5, 10 and 20 mg) and a PBO arm. Subjects will be randomized to receive one of three doses of volixibat (5, 10, or 20 mg once daily (QD) or PBO in a 1:1:1:1 ratio such that a target of 266 subjects is achieved (221x1.2 is approximately 266). The 221 subjects include 201 subjects for the three arms analyzed at 48 weeks plus an additional 20 subjects to account for one dose dropped at the IA). Attempt will be made to perform the IA before any subject has had their 48-week post-treatment liver biopsy, although this will be dependent upon the rate of enrollment and dropout.

There will be up to 3 periods (Screening, Treatment and Follow-up) and an IA. The duration of the Treatment period will be 48 weeks, with an IA at Week 24. Depending on the results of the IA, the study may be terminated or the randomization to one or more doses will be stopped. The follow-up period will be 4 weeks after last dose. Subjects will be expected to visit the study center at least 10 times.

The IA will be conducted by an independent data monitoring committee (DMC) after at least 80 subjects have received 24 weeks of treatment. Study enrollment will be paused after 92 subjects have been randomized. The IA will evaluate the safety, tolerability and efficacy of 3 doses of volixibat each compared to PBO, on reduction of steatosis as measured by high fat fraction (HFF) by MRI and ALT.

Once decisions as to dose elimination are made, study enrollment will be reopened and additional sites may be added. Subjects recruited into the study prior to the IA will continue with the same dosing regimen for the duration of the planned study participation. Subjects recruited into the study after completion of the IA will be randomized evenly to the remaining dose groups or PBO group by IRT. Thus, depending on the results from the IA, the study may be terminated, or one or more doses of volixibat will be discontinued. If the study is not terminated, subjects will receive a total of 48 weeks of investigational product (IP).

The study will be conducted over 3 periods: Screening (8 weeks), Treatment (48 weeks), and Follow-up (4 weeks), with an IA at 24 weeks as outlined in [Figure 1](#).

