4.5 Discontinuation of Subjects

A subject may withdraw from the study at any time for any reason without prejudice to their future medical care by the physician or at the institution. The investigator or sponsor may withdraw the subject at any time (eg, in the interest of subject safety). The investigator is encouraged to discuss withdrawal of a subject from the IP with the CRO Medical Monitor when possible.

If the IP is discontinued, regardless of the reason, the evaluations listed for both Visit 9/end of study (EOS) and Visit 10/Follow-up, are to be performed as completely as possible; however, the EOS liver biopsy will not be required for patients discontinuing prior to Week 44.

Comments (spontaneous or elicited) or complaints made by the subject must be recorded in the source documents. The reason for termination, date of stopping the IP, and the total amount of the IP taken must be recorded in the electronic case report form (eCRF) and source documents.

Subjects who discontinue will not be replaced.

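### Section 9.6 multiplies by 1.2 where a 20% dropout needs division by 0.8, so 266 randomised gives about 65 completers per arm, not 67

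*Protocol*

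**What the plan says.** The sample size chain is in Protocol Section 9.6.

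- The per-arm target: "The sample size target for this study is 67 completers in each of the treatment groups (201 total if 3 arms continue").
- The allowance for the dose dropped at the interim analysis: "Including an additional 20 subjects to account for one dose dropped at the IA, 221 subjects are needed".
- The dropout step: "Therefore, approximately 266 (accounts for 20% of 221 dropping out) subjects will be randomized if three arms (2 active and 1 PBO) continue".
- The summary of the chain: "Approximately 334 subjects will be screened to enroll 266 subjects to achieve 201 completers".
- On enrolment after the interim analysis, the same paragraph says that it will "continue to include approximately 67 subjects in each of the remaining arms", which counts subjects; the next sentence counts completers.

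Section 9.5.1 adds that "Study enrollment will be paused after 92 subjects have been randomized", about 23 per arm at equal allocation.

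The Amendment 1 text bound into the same file spells out the inflation in its Section 3.1: "221x1.2 is approximately 266". That text is superseded and is cited only to show where 266 came from. The current Section 9.6 carries the same total.

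**The concern.** A dropout rate is ordinarily a fraction of those randomised. To end with N completers at dropout rate d, one randomises N / (1 - d). Multiplying by (1 + d) gives too few, and at 20% the gap is visible. If that happened here, the headline figures (266 randomised, 201 completers, 67 per arm, 80% power) do not hold together. The 67 appears to have been sized with little to spare, so even a small shortfall takes the power claim just below 80% under the calculation that best reproduces it.

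The count of 67 subjects, one sentence before the count of 67 completers, adds to the confusion because the two describe different enrolment targets.

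**Working it through.** **Inputs (Section 9.6 unless noted).** 67 completers per arm; three continuing arms; 20 added for the dropped dose; 20% dropout; 266 randomised; 92 randomised before the pause (Section 9.5.1); response rates of 21% on placebo and 45% on active; 10% type I error with Holm over two doses; two-sided tests (Section 9.8).

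**Where 67 comes from.** The strictest Holm step is 0.10 / 2 = 0.05, two-sided. For 21% against 45% at 80% power, the normal-approximation formula gives 60 per arm uncorrected and 68 with continuity correction. The stated 67 is close to the corrected figure.

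**Where 266 comes from.**
- 3 x 67 = 201; 201 + 20 = 221.
- 221 x 1.2 = 265.2, rounded up to 266. This reproduces the plan.
- 221 / (1 - 0.20) = 276.25, rounded up to 277. This does not; it is 11 subjects more.

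**What 266 delivers.**
- Loss that still leaves 221: (266 - 221) / 266 = 45 / 266 = 16.9%.
- At 20% loss: 266 x 0.8 = 212.8 across all four arms, about 8 short of 221.

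The plan ties 201 to the three continuing arms, so the dropped arm comes off first. Its size is not fixed exactly, so three values were tried. Power is per comparison, two-sided 0.05, normal approximation.

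| Randomised to dropped arm | Left in three arms | Completers at 20% loss | Per arm | Power, continuity-corrected | Power, uncorrected |
|---|---|---|---|---|---|
| 20 | 246 | 196.8 | 65.6 | 78.9% | 84.0% |
| 23 (92 / 4) | 243 | 194.4 | 64.8 | 78.4% | 83.6% |
| 24 (20 x 1.2) | 242 | 193.6 | 64.5 | 78.1% | 83.4% |
| Plan's target | – | 201 | 67 | 79.9% | 84.8% |

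Fisher's exact test, computed over the full binomial distributions, gives 80.8% at 67 per arm and 79.2% at 65.

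**Check of the corrected total.** With 277 randomised and 20 to 25 in the dropped arm, the continuing arms give (277 - 20) x 0.8 = 205.6 down to (277 - 25) x 0.8 = 201.6 completers, that is 68.5 down to 67.2 per arm. The target is met throughout.

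**The case against.** **The sentence is literally consistent.** It speaks of 20% of 221. That is 44.2, and 221 + 44.2 = 265.2. The protocol does not separately state a 20% rate among those randomised. This stands as a reading of the words. It means, however, that the allowance is about 17% of those randomised, which the section never says and which a reader will not take from a 20% figure.

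**Total completers exceed 201.** 212.8 is above 201, but only if completers on the dropped dose are counted. Section 9.6 adds those subjects separately from the 201.

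**The effect is slight and the figure is approximate.** This stands. The shortfall is 1.4 to 2.5 completers per arm. The alternative hypothesis in Section 9.6 needs only one dose to differ. If both doses respond at 45%, the chance of at least one Holm rejection is about 94% uncorrected and 91% continuity-corrected at 65 per arm, against 94.5% and 92% at 67. No conclusion of the trial turns on 65 versus 67.

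**Two stronger readings are tempting, and the protocol supports neither.**
- *The dropped-dose allowance should be 23, not 20, because 92 are randomised before the pause.* The 20 enters before inflation. Inflated the plan's way it becomes 20 x 1.2 = 24, which already covers 92 / 4 = 23. The shortfall does not depend on this choice.
- *Enrolment might stop at 67 randomised per arm, leaving about 54 completers (67 x 0.8 = 53.6) and power near 70%.* The next sentence sets the target in completers, and 3 x 67 plus 20 to 23 is 221 to 224, which cannot be squared with 266 randomised. The wording is loose, but the paragraph settles its meaning.

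**Conclusion.** The inflation step is wrong for a 20% dropout rate in its usual sense. The stated 266 protects against about 17% loss. At 20% it leaves about 194 to 197 completers in the three continuing arms, about 65 each, against 201 and 67.

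Per-comparison power at the first Holm step falls by about 1 to 2 points: just under 80% with continuity correction or Fisher's exact test, and still near 84% without correction.

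This rests on four assumptions: 20% is a fraction of those randomised; dropout is equal across arms; the dropped arm holds 20 to 24 subjects; and the response rates are those the plan assumes. It also takes dropouts as lost. The Amendment 1 text (Section 4.5) says "Subjects who discontinue will not be replaced"; the current Section 4.5 is not in the part of the protocol available here.

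Severity is minor. It is an arithmetic slip in the headline sample size statement that is cheap to correct; it does not undermine the design.

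**What to change.** Keep 266 and restate Section 9.6, and the synopsis where it repeats the figure, in one of two ways:

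- 266 randomised allows for a dropout of about 17% among those randomised and targets 67 completers per arm; or
- at 20% dropout, 266 randomised gives about 65 completers in each of the three continuing arms, with per-comparison power restated to match and the calculation method named.

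Either way, change the sentence on enrolment after the interim analysis from 67 subjects to 67 completers in each remaining arm (or to the restated figure), so that it agrees with the sentence that follows. Leave the 20 for the dropped dose as it is.

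The cost is a few words and, under the second option, a slightly less favourable power statement. No extra patients are needed. If the sponsor prefers to keep both 67 completers and 20% dropout, the plan's own formula gives 277 randomised, 11 more. The screening figure would then rise in proportion, from 334 to about 348 (277 x 334 / 266 = 347.8).

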9.7 Study Population

The Screened Set will consist of all subjects who have signed an informed consent.

The Safety Analysis Set will consist of all subjects who take at least 1 dose of randomized IP, and have at least 1 post-baseline safety assessment (eg, coming back for any visit, reporting of an AE or reporting the absence of AEs).

The Full Analysis Set (FAS) will consist of all subjects in the Safety Analysis Set who have at least 1 post-baseline efficacy assessment (eg, MRI, liver biopsy, serum liver-related biochemistry measurement).

The Interim Analysis Set (IAS) will consist of all subjects in the Safety Analysis Set who have at least 1 post-baseline efficacy assessment (eg, MRI, ALT biochemistry measurement) on or before the Week 24 visit at the data cut time of the IA.

9.8 Efficacy Analyses

All efficacy analyses will be based on the FAS and all statistical tests will be 2-sided hypothesis tests performed at the 10% level of significance. Also, all confidence intervals will be 2-sided confidence intervals, unless otherwise stated.

9.8.1 Primary Efficacy Endpoint

The primary endpoint is the binary response indicating (yes/no) whether a subject responded at Week 48 with a reduction of at least 2 points, without worsening of fibrosis, from baseline NAS.

The FAS will be used to assess the primary efficacy endpoint. The proportion of subjects at Week 48 with a reduction of at least 2 points without worsening of fibrosis from baseline NAS will be analyzed. The difference between a volixibat dose and PBO will be tested with a stratified Cochran-Mantel-Haenzel test. The test will be stratified by presence or absence of T2DM at baseline and baseline NAS separated into two groups (NAS={4, 5} or NAS={6,7,8}). Holm multiplicity adjustment will be applied prior to determining statistical significance at the 0.1 level.

Analyses which explore the impact of the missing data on the primary efficacy endpoint will be conducted. These analyses may compare imputations of the missing values which favor the PBO and/or imputations which favor the active. In addition, analyses utilizing existing HFF and/or ALT data may be performed. Further, if the pattern of missing values does not appear uniformly distributed among the treatment arms, imputation method(s) based on informative missingness

may also be performed. Analyses investigating the impact of missing data will be detailed in the Statistical Analysis Plan.

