6.2.2 Allocation of Subjects to Treatment

This is a double-blind, PBO-controlled study. The actual treatment given to individual subjects is determined by a randomization schedule.

Subject numbers are assigned to all subjects as they consent to take part in the study. Within each site (numbered uniquely within a protocol), the subject number is assigned to subjects according to the sequence of presentation for study participation.

The randomization number represents a unique number corresponding to the IP allocated to the subject, once eligibility has been determined.

Individual subject treatment is automatically assigned by the IRT.

Once a randomization number/unique identifier has been assigned, that number must not be used again if, for example, a subject is withdrawn from the study. If a randomization number/unique identifier is allocated incorrectly, the clinical research associate (CRA)/study monitor must be notified as soon as the error is discovered.

IP packaging identification numbers, separate from randomization numbers/unique identifiers, may also be assigned to subjects for specific treatment assignment as dictated by the study. In these cases, the same IP packing identification number may not be assigned to more than 1 subject.

Subjects will be equally allocated to all volixibat doses and PBO if their randomization precedes the 24 week IA. If a subject's randomization occurs after the 24 week IA, subjects will be equally allocated to all remaining volixibat doses (determined based on the results of the IA) and PBO. The randomization will be stratified by baseline T2DM and NAS ≥ 6 or NAS = {4, 5}.

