9.8.2 Secondary Efficacy Endpoints

Descriptive statistics will be presented for each time point at which the variable is measured (see [Table 1](#)) for the secondary efficacy endpoints. Binary secondary efficacy endpoints will be analyzed with the same method (stratified Cochran-Mantel-Haenzel test) as the primary efficacy endpoint. Continuous secondary efficacy endpoints will be analyzed with an ANCOVA model with change from baseline as the outcome variable; treatment group, presence or absence of T2DM at baseline, and baseline NAS separated into 2 groups (NAS={4,5} or NAS={6,7,8}) as factors and baseline values as a covariate. Endpoints include:

- Change from baseline to Week 48 on liver histology as measured by the individual NAS components (ballooning, inflammation, steatosis).
- Change from baseline to Week 48 on hepatic steatosis as measured by MRI-HFF.
- Change from baseline to Week 48 on liver histology as measured by fibrosis stage. (NASH CRN)
- Resolution of NASH (defined as an overall histologic interpretation of no fatty liver disease or simple steatosis without steatohepatitis or isolated steatosis without steatohepatitis) without worsening of fibrosis as assessed by liver histology at Week 48.
- Change from baseline to Week 48 on serum liver-related biochemistry as measured by:
 - alanine aminotransferase (ALT)
 - aspartate aminotransferase (AST)
 - alkaline phosphatase (ALP)
 - gamma glutamyl transferase (GGT)
 - total bilirubin (TB)
- Change from baseline to Week 48 on metabolic indicators as measured by:
 - fasting serum glucose levels
 - insulin levels
 - HbA1c
- Change from baseline to Week 48 on serum lipids measured by:
 - fasting total cholesterol

- HDL-C
- LDL-C
- triglycerides

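### If the dose closed at the interim is compared with placebo under Sections 9.8.1 to 9.8.3 as written, about 72% of its placebo control was randomised after it closed, with no adjustment for drift

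*Protocol*

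**What the plan says.** - **Allocation changes at the interim.** Section 6.2.2: "Subjects will be equally allocated to all volixibat doses and PBO if their randomization precedes the 24 week IA". For later subjects, "subjects will be equally allocated to all remaining volixibat doses (determined based on the results of the IA) and PBO". Section 9.5.1 sets the break between the two periods: "Study enrollment will be paused after 92 subjects have been randomized".
- **At least one dose closes if the trial continues.** Under Section 9.5.1, later subjects go to one or two doses or placebo. Even if no dose fails, the least promising or least informative one is closed.
- **The closed dose is followed up.** Section 9.5.1: "a subject receiving a dose to which randomization is stopped after the IA will continue to receive that same dose". Its subjects complete all assessments, including the Week 48 biopsy, unless the dose is judged unsafe.
- **Analysis set.** The FAS in Section 9.7 excludes no arm and no period. Section 9.8 bases all efficacy analyses on it.
- **Primary test.** Section 9.8.1: "The difference between a volixibat dose and PBO will be tested with a stratified Cochran-Mantel-Haenzel test". The strata are diabetes at baseline and NAS group. The null in Section 9.6 covers any of the doses. Holm adjustment is applied at 0.1.
- **Continuous endpoints.** Section 9.8.2: "Continuous secondary efficacy endpoints will be analyzed with an ANCOVA model with change from baseline as the outcome variable". The factors are treatment group, diabetes and NAS group, with the baseline value as covariate. Section 9.8.3 repeats this.

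These sections neither separate subjects randomised before and after the interim nor limit the placebo group to concurrent subjects.

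**The concern.** A subject randomised to placebo after the interim could not have been allocated to the closed dose. Comparing that dose with the whole placebo arm therefore sets early subjects against a control group recruited mostly later, after a pause and possibly at other sites. Randomisation does not protect that contrast. A shift over time in case mix, sites or biopsy reading would appear as an effect of the dose, favourable or unfavourable. In a dose-finding trial the closed dose is one of three points on the dose-response, and it may have been closed only because it was the least informative of three acceptable doses.

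**Working it through.** **The plan's own figures.** For 21% against 45%, 80% power and two-sided 0.05 (0.10/2, the first Holm step for two doses), the continuity-corrected formula gives 68 per group, close to the stated 67 (60 without the correction). Then 3 × 67 + 20 = 221, and 221 × 1.2 = 265.2, matching Section 9.6: "approximately 266 (accounts for 20% of 221 dropping out) subjects will be randomized if three arms (2 active and 1 PBO) continue".

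**Share of placebo that is non-concurrent, one dose closed.**
- Placebo before the interim: 92/4 = 23.
- Placebo after it: (266 − 92)/3 = 58.
- Share: 58/(23 + 58) = 58/81 = 71.6%.
- On the completer basis of Section 9.6 ("After enrollment of at least 80 subjects (20/treatment arm", rising to 67): 47/67 = 70%.
- Over 80 or 92 subjects before the interim and totals of 221, 266 or 277 (277 being 221/0.8), the share runs from 65% to 76%.

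**Bias.** Let early placebo respond at rate p and late placebo at p − d, with n1 early and n2 late placebo subjects. A closed dose with no effect responds at p. The expected difference from pooled placebo is

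p − [n1·p + n2·(p − d)]/(n1 + n2) = d × n2/(n1 + n2) = 0.716·d.

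A 5-point fall gives +3.6 points and a 10-point fall +7.2; equal rises give the same with a minus sign.

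**False rejection of a closed dose with no effect.** Assumptions: 18 completers on the dose, 18 early and 47 late on placebo (roughly 80% of 23, 23 and 58; 47/65 = 72%); early rate 21%; uncorrected chi-square test without the diabetes and NAS strata. The drift sizes are assumptions, since the protocol gives none.

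| Late placebo rate | two-sided 0.10 | 0.05 | 0.033 |
|---|---|---|---|
| 11% (10-point fall) | 21.6% | 14.3% | 10.1% |
| 31% (10-point rise) | 15.4% | 8.0% | 5.0% |

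The 0.033 column is the first Holm step if three doses are tested (0.10/3). After a fall, nearly all rejections favour the drug. After a rise, nearly all go against it: of the 15.4%, only 1.2 points favour the drug. For falls of 5 and 15 points the rates are 13.6% and 35.9% at 0.10, and 5.1% and 20.5% at 0.033. With no drift the 0.10 test rejects 10.6% of the time; against concurrent placebo only, 9.9%.

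**Retained doses.** Each has the same expected mix as placebo, 23 early and 58 late, so drift cancels from the difference.

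**Power for the closed dose, 21% against 45%, two-sided 0.05, no drift.** About 63% with 23 against 81 and about 41% with 23 against 23.

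**The case against.** The strongest reply is that the protocol never expressly plans a final test of the closed dose. Section 9.6 sizes and Holm-adjusts for two doses against placebo and counts the closed arm only as 20 extra subjects. The superseded Amendment 1 text (Section 3.1) speaks of three arms analysed at Week 48. The opening sections of the current amendment and any SAP are not shown, and a SAP could settle the Holm family and the control group. This stands, and it is why the point is conditional. A reader might infer that a test of the closed dose against all placebo is laid down; the text does not go that far. But sizing for two doses does not exclude the third. The FAS, the wording of Section 9.8.1, the null and the treatment factor in the ANCOVA all take it in, and the protocol itself fixes strata and factors that omit period.

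Three further limits also stand:

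- The 21.6% is not the error rate at the first Holm step. If the closed dose is in the family, the family has three members and 0.10 applies only after both other doses are rejected.
- The pause need not last 24 weeks, as a reader might infer. Enrolment stops at 92 subjects but the interim needs only 80 with 24 weeks of treatment, and the 80th may have been randomised before the 92nd.
- A dose closed as unsafe has its subjects discontinued, leaving few or no Week 48 biopsies to compare.

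**Conclusion.** The point holds conditionally. Followed as written, Sections 9.8.1 to 9.8.3 would compare the closed dose with a placebo group that is about 72% non-concurrent, with no adjustment, and the bias is about 0.72 times whatever drift occurs. The share rests on equal allocation, 92 subjects before the interim, 266 in total and one dose closed. The rejection rates also rest on assumed drift, completer numbers and an unstratified test. For a 10-point fall they are roughly two to three times nominal.

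A reader might infer that the trial's main conclusions are at risk. They are not on this account: the retained doses are balanced with placebo in both periods. The damage is confined to one small arm and to how its place in the dose-response is read. This is a cheap improvement, not a defect in the comparisons for which the trial is powered.

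**What to change.** - In Section 9.8.1, add randomisation period (before or after the interim) as a stratum of the Cochran-Mantel-Haenszel test. The later strata contain no closed-dose subjects, so they drop out of that comparison.
- In Sections 9.8.2 and 9.8.3, add period as an ANCOVA factor. This removes the drift provided that it shifts all arms equally.
- Alternatively, compare the closed dose only with placebo subjects randomised before the pause, which does not need that assumption.
- State whether the closed dose belongs to the Holm family or is reported descriptively.

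**Cost.** A sentence or two in the protocol, carried into the SAP. Strata rise from four to eight and become smaller, which the Cochran-Mantel-Haenszel test tolerates. With concurrent placebo only, nominal power for the closed dose falls from about 63% to about 41%; the power given up came from controls not randomised alongside it. The retained-dose comparisons are essentially unaffected.
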